3.6 Risks and benefits

Initially, patients have a 75% chance to be treated with a potentially efficacious treatment for a chronic disease with possible long term outcomes including serious disabilities. Patients who receive placebo up to week 24 in period 2 will receive active treatment with VAY736 in period 3. Patients who are on placebo in period 2 and are being discontinued prior to week 24 for any reason will not be eligible to receive active treatment in period 3. The study is designed to limit exposure to placebo. However, for the 25% of patients who will receive placebo in period 2, no other approved systemic therapy exists, and thus i) certain background therapy is allowed during the trial and ii) in period 3, the opportunity of receiving active treatment.

As VAY736 is a systemic immunosuppressive treatment, the study population will be limited to include patients with moderate-to-severe pSS who are most likely to benefit from such a therapy. Based on a risk/benefit evaluation it was concluded that very severely ill patients with high steroid requirements (>10 mg/day prednisone or equivalent) or in need of immunosuppressive treatments such as cyclophosphamide, should not be included in this first multiple dose study of VAY736 in pSS. Hence, these medications are disallowed to be used concomitantly ([Table 5-1](#)).

Acute injection reactions: First-dose mild-to-moderate injection reactions were observed in the phase 1/2a studies in a substantial subset of patients.

Therefore,

[REDACTED] a mandatory pre-medication with i.v. methylprednisolone (with or without additional antihistamine and/or paracetamol medication at the discretion of the investigator) prior to the first VAY736 dose will be administered in the current trial.

Infections: At the time of protocol amendment, no SAEs related to infections have been observed in VAY736 exposed patients (during/after VAY736 exposure) in the ongoing or completed VAY736 clinical trials. An increase in mild-to-moderate upper respiratory tract infections compared to placebo has been associated with use of VAY736.

[REDACTED]

Neutropenia:

Late onset neutropenia (LON)

[REDACTED]

So far, no cases of LON were observed in VAY736 exposed patients after dosing.

Monitoring: Patients are required to stay at the clinic until at least 6 hours after first study medication (particular requirements for Japan; [Section 5.5](#)). Patients should be clinically monitored during this period. Patients should be instructed to promptly report symptoms occurring within 24 hours after study drug administration.

Potential safety risks will be monitored by routine assessments, including complete physical examination (with emphasis on salivary/parotid gland and lymph node assessments in the head/neck region, and inspection of the mouth including teeth and gums), and standard laboratory assessments to occur at all scheduled site visits (every 4 weeks). No specific safety monitoring measures beyond routine monitoring will be taken, [REDACTED]

[REDACTED] In the current trial, the safety assessments selected are standard for this indication and patient population. In addition, IgG and IgM levels will be monitored in regular intervals.

[REDACTED]

Allergic reactions: Although no allergic reactions following i.v. or s.c. administration were observed so far, the potential to develop an allergic reaction in a predisposed subject cannot entirely be ruled out. Routine monitoring as for other biological treatments is warranted, as described in IB.

Vaccinations: In immune suppressed patients, live vaccinations may cause serious adverse events and vaccination success may be attenuated. No data exists on the effect of VAY736 on response to vaccinations in general. Study subjects should receive appropriate vaccinations

before entering the study in accordance with current immunization guidelines at least 4 weeks prior to study medication administration, noting that randomization should not occur less than 2 months after a live vaccine is given. For further information please refer to Vaccination Guidance for VAY736 (provided to study sites).

[figure not shown]
Although no signs and symptoms of immunogenicity have been observed so far, administration of mAb, independent of the antibody specificity for antigen, carries the risk of immune reactions such as acute anaphylaxis, serum sickness and the generation of anti-drug antibodies. Other clinical manifestations can include local skin reactions at the injection site, pyrexia and an influenza-like syndrome.

Potential side-effects of the methylprednisolone pre-medication are short-term and may include sodium retention-related weight gain and fluid accumulation, hyperglycemia and glucose intolerance, hypokalemia, gastrointestinal upset. These symptoms are generally self-limiting and do not require treatment. Patients with uncontrolled diabetes or hypertension will be excluded from the trial to avoid any risk in these patients.

The risk for patients in this trial will be minimized by compliance with the eligibility criteria and study procedures, close clinical monitoring, and compliance with criteria for treatment interruption outlined in the protocol. Drug-drug interactions are unlikely with biologics, however, sites and patients must strictly observe and adhere to the list of prohibited medications listed in the protocol ([Section 5.5.8](#)).

4 Population

The study population will consist of male and female patients aged 18 to 75 years with pSS defined according to the revised American European Consensus Group (AECG) classification criteria ([Vitali et al., 2002](#)), and moderate to severe active disease defined as: (i) having an ESSDAI score ≥ 6 within the following 7 domains: biologic, hematologic, articular, cutaneous, glandular, constitutional and lymphadenopathy (a subset of at least 30% of patients must have an ESSDAI ≥ 10). Patients also having involvement of one or more of the remaining five domains are eligible. Eligible patients must fulfill all inclusion and exclusion criteria. The goal is to randomize a total of approximately 180 patients at approximately 90 centers worldwide, including North America and Europe. Since a 50% screening failure rate is expected, approximately 360 patients will be screened.

4.1 Inclusion criteria

Patients eligible for inclusion in this study must fulfill all of the following criteria:

1. Written informed consent (IC) must be obtained before any assessment is performed
2. Male and female patients aged 18 to 75 years
3. Fulfilled revised American European Consensus Group criteria for pSS ([Vitali et al., 2002](#)); if key inclusion criteria are missing from medical history, information will be obtained at screening and may be used as a baseline value if required
4. ESSDAI value ≥ 6 at screening, based on weighted scores of the 7 domains: biologic, hematologic, articular, cutaneous, glandular, lymphadenopathy and constitutional domains
5. ESSPRI value ≥ 5 at baseline
6. Seropositive at screening for anti-Ro/SSA antibodies
7. Stimulated whole salivary flow rate at screening of >0.1 mL/min
8. Able to communicate well with the investigator, to understand and comply with the requirements of the study

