4.2 Exclusion criteria

Patients fulfilling any of the following criteria are not eligible for inclusion in this study. No additional exclusions may be applied by the investigator, in order to ensure that the study population will be representative of all eligible patients.

1. Use of other investigational drugs within 5 half-lives of enrollment or within 30 days whichever is longer, or longer if required by local regulations
2. Secondary Sjögren's syndrome (presence of another connective tissue disease)
3. Prior use of any B-cell depleting therapy (e.g., rituximab or other anti-CD20 mAb, anti-CD22 mAb or anti-CD52 mAb)
 - within 1 year prior to randomization
 - or as long as B-cell count <50 cells/ μ L
4. Current use of prednisone >10 mg/day [or equivalent other corticosteroid] or dose change within 2 weeks prior to randomization
5. Prior treatment with any of the following within 180 days prior to randomization (anti-BAFF mAb; CTLA4-Fc Ig (abatacept); anti-TNF- α mAb; intravenous/subcutaneous Ig; plasmapheresis; i.v. or oral cyclophosphamide; oral cyclosporine)
 - Patients taking either hydroxychloroquine or methotrexate or azathioprine at consistent dose for ≥ 3 months prior to randomization are eligible if dose is maintained throughout the study
 - If azathioprine is discontinued prior to enrollment, a minimum washout period of 30 days prior to randomization is required.
6. Active viral, bacterial or other infections requiring systemic treatment at the time of screening or enrollment, or history of recurrent clinically significant infection or of bacterial infections with encapsulated organisms
7. History of major organ, hematopoietic stem cell or bone marrow transplant

8. History of hypersensitivity to any of the study drugs or to drugs of similar chemical classes (e.g., mAb of IgG1 class) or to any of the constituents of the study drug (sucrose, L-Arginine hydrochloride, L-histidine, polysorbate 80, hydrochloric acid)
9. Required regular use of medications known to cause dry mouth/eyes as a regular and major side effect
10. Receipt of live/attenuated vaccine within a 2 month period before baseline
11. History of primary or secondary immunodeficiency, including a positive HIV (ELISA and Western blot) test result

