9.4.4 Sensitivity analyses

To assess the potential influence of adherence to study procedures on the results of the primary analysis in the subset of patients more compliant with protocol requirements the following sensitivity analysis will be conducted: The full dose response modeling analysis as described in [Section 9.4.2](#) will be repeated only including data of patients who have no protocol deviations that are expected to potentially confound the interpretation of primary analysis. These major protocol deviations will be identified from those included in the validation analysis plan prior to database lock and the unblinding of the study.

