#### 5.5 Rule of exclusion criteria of analysis sets

**Table 5-4 Protocol deviations that cause subjects to be excluded from PP analysis**

Deviation ID	Description of Deviation
INCL03 & INCL06	No histology biopsy and negative serology at screening for [REDACTED]
INCL04	ESSDAI value <6 at screening, based on weighted scores of the 7 domains: biologic, hematologic, articular, cutaneous, glandular, lymphadenopathy and constitutional domains
INCL05	ESSPRI value <5 at baseline
TRT01	Patient did not receive at least one dose of study medication
TRT02	Patient received wrong study medication
TRT03	Patient missed two consecutive doses of study medication
CONC01	Use of other investigational drugs within 5 half-lives of enrollment or within 30 days whichever is longer, or longer if required by local regulations

[figure not shown]
Deviation ID	Description of Deviation
CONC02	Prior use of any B-cell depleting therapy (e.g., rituximab or other anti-CD20 mAb, anti-CD22 mAb or anti-CD52 mAb) 

• within 1 year prior to randomization

• or as long as B-cell count <50 cells/<math>\mu</math>L

CONC03	Prior treatment with any of the following within 180 days prior to randomization [REDACTED] CTLA4-Fc Ig (abatacept); anti-TNF- $\alpha$ mAb; intravenous/subcutaneous Ig; plasmapheresis; i.v. or oral cyclophosphamide; oral cyclosporine 

• Patients taking either hydroxychloroquine or methotrexate or azathioprine at consistent dose for <math>\geq</math>3 months prior to randomization are eligible if dose is maintained throughout the study

• If azathioprine is discontinued prior to enrollment, a minimum washout period of 30 days prior to randomization is required.

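### SAP Table 5-4 merges inclusion criteria 3 and 6 into one joint per-protocol exclusion, so a patient who fails only one of them can stay in the per-protocol set

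*Protocol*

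**What the plan says.** Protocol 4.1 opens its list with "Patients eligible for inclusion in this study must fulfill all of the following criteria". Item 3 is "Fulfilled revised American European Consensus Group criteria for pSS". Item 6 is "Seropositive at screening for anti-Ro/SSA antibodies". They are separate items, and item 6 does not let a biopsy stand in for serology. The protocol summary also lists seropositivity as a key criterion of its own.

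Protocol 9.4.4 plans a repeat of the full dose-response analysis in patients "who have no protocol deviations that are expected to potentially confound the interpretation of primary analysis", with those deviations identified before database lock and unblinding. SAP 2.2 defines the per-protocol set as the FAS less patients with major deviations, and SAP 2.5.3 commits to repeating the dose-response analysis on that set.

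The deviations are listed in SAP 5.5, Table 5-4. One row carries the identifier "INCL03 & INCL06" and the condition "No histology biopsy and negative serology at screening for", followed by a redacted term. The next two rows, INCL04 and INCL05, each state the failure of a single criterion, for example "ESSPRI value <5 at baseline". No other visible row deals with serology or AECG classification.

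**The concern.** A per-protocol set is useful for checking the influence of ineligible patients only if its exclusion rules match the criteria they name. This row names two mandatory criteria but removes a patient only when a joint condition holds, and that condition is narrower than failing either criterion. Some patients who break item 6, and some who break item 3, then stay in the analysis that is meant to be run without them.

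A second problem is that the biopsy phrase can be read in two ways: no biopsy was done, or no biopsy supported the diagnosis. Two programmers could build two different sets. If the meaning is settled after unblinding, membership of the set becomes a post-hoc choice, which Protocol 9.4.4 is meant to prevent.

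**Working it through.** The plan gives no figure to reproduce, so the check is a comparison of rules.

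**Step 1: does the row refer to protocol items 3 and 6?** The antibody name is redacted, so the link rests on the identifiers. INCL04 in Table 5-4 is the failure of protocol item 4 (ESSDAI threshold) and INCL05 is the failure of item 5 (ESSPRI threshold). By the same numbering, INCL03 is AECG classification and INCL06 is anti-Ro/SSA serology.

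**Step 2: apply each rule to seronegative patients.** All of them break item 6. They differ only in biopsy status.

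| Biopsy status (seronegative patient) | Breaks item 6 | Removed by the row as worded | Removed if the row means no supporting histology | Removed by item 6 alone |
|---|---|---|---|---|
| None done | Yes | Yes | Yes | Yes |
| Done, negative | Yes | No | Yes | Yes |
| Done, positive | Yes | No | No | Yes |
| States removed | – | 1 of 3 | 2 of 3 | 3 of 3 |

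On both readings a seronegative patient with a positive biopsy stays in. The negative-biopsy case depends on which reading is intended.

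**Step 3: apply the row to a seropositive patient who fails AECG.** The row requires negative serology, so it cannot remove this patient whatever the biopsy shows. No other visible row covers item 3.

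**Step 4: compare with the neighbouring rows.** INCL04 and INCL05 are each the plain negation of one criterion, and each is sufficient alone. The merged row is the only inclusion row whose condition is weaker than the criteria it cites.

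**Step 5: trace where the set is used.** Protocol 9.4.1 and SAP 2.5.1 base the primary analysis on the FAS. The per-protocol set enters the supportive repeat in SAP 2.5.3. The primary estimate, its alpha and the sample size do not depend on Table 5-4.

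**Step 6: how many patients?** The documents give no count of seronegative patients, of biopsied patients or of AECG failures. The effect on the per-protocol estimate cannot be computed from them.

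**The case against.** The strongest reply is that the protocol never promised to remove every ineligible patient. Section 9.4.4 asks only for deviations that could confound the primary analysis, and SAP 2.2 speaks of major deviations. On this view the joint row is a deliberate choice: exclude only when both diagnostic supports are missing. The protocol does treat biopsy as diagnostic information; the heading of 6.2.4 says so, and 9.2 summarises positive biopsy results.

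Part of this stands. The sponsor has discretion over which deviations exclude, and because 9.4.4 fixes no list, the SAP's statement that nothing changed from the protocol is not contradicted by this row. But the SAP used its discretion by naming INCL06 as an excluding deviation, and then wrote a condition that does not match that criterion. If biopsy is meant to offset negative serology, neither document says so, gives a reason or states what result would be needed.

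Other controls also count. Under Protocol 5.3 sites contact the IRT after confirming eligibility, Protocol 8.1 requires full verification of adherence to the entry criteria, and SAP 2.3.1 tabulates major deviations. These make affected patients less likely and more visible. They do not correct the rule.

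Three stronger readings are tempting, and the documents do not support them:

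- **That a negative biopsy certainly keeps a seronegative patient in.** This holds only on the literal wording. The phrase may be loose shorthand for no supporting histology.
- **That the table must also cover exclusion 2 (secondary Sjögren's syndrome) and exclusion 4, "Current use of prednisone >10 mg/day [or equivalent other corticosteroid] or dose change within 2 weeks prior to randomization".** No visible row does. But the table is visibly selective (inclusion 7 and exclusions 6 to 19 have no visible row either), parts of it are redacted, and 9.4.4 permits selection. Adding those rows would be a preference.
- **That the retained patients dilute the treatment effect by a calculable amount.** Any such figure needs a patient count and an assumption that seronegative patients do not respond. The documents supply neither.

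**Conclusion.** The point holds as a mismatch between a stated SAP rule and the two protocol criteria it cites. On either reading of the biopsy phrase, a seronegative patient with a positive biopsy stays in the per-protocol set despite breaking item 6, and a seropositive patient who fails AECG stays in despite breaking item 3.

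Its reach is limited to the supportive per-protocol dose-response analysis. The number of patients involved is unknown and may be zero, so no bias in the result is claimed. The conclusion assumes that the identifiers follow the protocol numbering, as INCL04 and INCL05 do, and that no redacted text in Table 5-4 restores the two criteria as separate exclusions. It is worth correcting because the rule builds the wrong set, can be read in two ways and costs almost nothing to repair.

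**What to change.** Before database lock, replace the merged row in SAP Table 5-4 with two rows, each sufficient for exclusion from the per-protocol set:

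- INCL03: AECG criteria not fulfilled.
- INCL06: not seropositive at screening for anti-Ro/SSA.

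This gives them the same form as INCL04 and INCL05. If the sponsor does intend a biopsy to offset negative serology in this set, the SAP should instead say so, justify it and define the biopsy result required.

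The same edit can correct the pointer in SAP 2.2, which sends the reader to Section 5.6 (steroid conversion) for deviations that are listed in Section 5.5.

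The cost is a change of table wording. The downside is a slightly smaller per-protocol set if any such patients were randomized. No change to the primary analysis or to data collection is needed.

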4.2 Exclusion criteria

Patients fulfilling any of the following criteria are not eligible for inclusion in this study. No additional exclusions may be applied by the investigator, in order to ensure that the study population will be representative of all eligible patients.

1. Use of other investigational drugs within 5 half-lives of enrollment or within 30 days whichever is longer, or longer if required by local regulations
2. Secondary Sjögren's syndrome (presence of another connective tissue disease)
3. Prior use of any B-cell depleting therapy (e.g., rituximab or other anti-CD20 mAb, anti-CD22 mAb or anti-CD52 mAb)
 - within 1 year prior to randomization
 - or as long as B-cell count <50 cells/ μ L
4. Current use of prednisone >10 mg/day [or equivalent other corticosteroid] or dose change within 2 weeks prior to randomization
5. Prior treatment with any of the following within 180 days prior to randomization (anti-BAFF mAb; CTLA4-Fc Ig (abatacept); anti-TNF- α mAb; intravenous/subcutaneous Ig; plasmapheresis; i.v. or oral cyclophosphamide; oral cyclosporine)
 - Patients taking either hydroxychloroquine or methotrexate or azathioprine at consistent dose for ≥ 3 months prior to randomization are eligible if dose is maintained throughout the study
 - If azathioprine is discontinued prior to enrollment, a minimum washout period of 30 days prior to randomization is required.
6. Active viral, bacterial or other infections requiring systemic treatment at the time of screening or enrollment, or history of recurrent clinically significant infection or of bacterial infections with encapsulated organisms
7. History of major organ, hematopoietic stem cell or bone marrow transplant

8. History of hypersensitivity to any of the study drugs or to drugs of similar chemical classes (e.g., mAb of IgG1 class) or to any of the constituents of the study drug (sucrose, L-Arginine hydrochloride, L-histidine, polysorbate 80, hydrochloric acid)
9. Required regular use of medications known to cause dry mouth/eyes as a regular and major side effect
10. Receipt of live/attenuated vaccine within a 2 month period before baseline
11. History of primary or secondary immunodeficiency, including a positive HIV (ELISA and Western blot) test result
12. History of malignancy of any organ system (other than localized basal cell carcinoma of the skin, *in situ* cervical cancer or pSS related lymphoma), treated or untreated, within the past 5 years, regardless of whether there is evidence of local recurrence or metastases
13. History of sarcoidosis
14. Any one of the following screening values of CBC laboratory values: Hemoglobin levels below 8.0 g/dL; Total leukocyte count less than 2,000/ μ L; Platelets <100.0 \times 10⁹/L; Absolute neutrophil count (ANC) <1.5 \times 10⁹/L (one re-test is allowed during the screening period)
15. Any surgical, medical (e.g., uncontrolled hypertension, heart failure or diabetes), psychiatric or additional physical condition that the Investigator feels may jeopardize the patient in case of participation in this study
16. Positive hepatitis B surface antigen (HBsAg), antiHB core antigen (anti-HBc) or anti-HB surface antigen (anti-HBs) or positive hepatitis C test result (Patients positive for anti-HBs after Hep B vaccination but negative for HBsAg and anti-HBc are eligible; [Table 19-1](#))
17. Evidence of active tuberculosis (TB) infection (after anti-TB treatment, patients with history of or latent TB may become eligible according to national guidelines)
18. Pregnant or nursing (lactating) women, where pregnancy is defined as the state of a female after conception and until the termination of gestation, confirmed by a positive hCG laboratory test
19. Women of child-bearing potential (WOCBP), defined as all women physiologically capable of becoming pregnant, unless they are using highly effective methods of contraception during dosing and for 4 months after stopping of investigational medication. Highly effective contraception methods include:
 - a. Total abstinence (when this is in line with the preferred and usual lifestyle of the patient). Periodic abstinence (e.g., calendar, ovulation, symptothermal, post-ovulation methods) and withdrawal are not acceptable methods of contraception
 - b. Female sterilization (have had surgical bilateral oophorectomy with or without hysterectomy) total hysterectomy or tubal ligation at least six weeks before taking investigational drug. In case of oophorectomy alone, only when the reproductive status of the woman has been confirmed by follow up hormone level assessment
 - c. Male sterilization (at least 6 months prior to screening and confirmed as successful). For female patients in the study, the vasectomized male partner should be the sole partner for that patient
 - d. Use of oral, (estrogen and progesterone), injected or implanted hormonal methods of contraception or placement of an intrauterine device (IUD) or intrauterine system

(IUS) or other forms of hormonal contraception that have comparable efficacy (failure rate <1%), for example hormone vaginal ring or transdermal hormone contraception. In case of use of oral contraception women should have been stable on the same pill for a minimum of 3 months before taking investigational drug.

Women are considered post-menopausal and not of child bearing potential if they have had 12 months of natural (spontaneous) amenorrhea with an appropriate clinical profile (e.g., age appropriate, history of vasomotor symptoms) or have had surgical bilateral oophorectomy (with or without hysterectomy), total hysterectomy or tubal ligation at least six weeks ago. In the case of oophorectomy alone, only when the reproductive status of the woman has been confirmed by follow up hormone level assessment is she considered not of child bearing potential.

5 Treatment

